### **9.1.2. Sensitivity Analyses**

Not applicable.

### **9.1.3. Subgroup Analyses**

The influence of baseline and demographic characteristics on the treatment effect may be explored via exploratory subgroup analyses if the number of subjects in a subgroup category is  $\geq 5$ .

## **9.2. Secondary Efficacy Endpoints and Analyses**

### **9.2.1. Duration of Response (DOR)**

The investigator-assessed objective response will be further characterized by the DOR. DOR will be evaluated for responders (confirmed CR and PR) only.

DOR is defined as the time (months) from first confirmed response (CR or PR) to the date of the first documented tumor progression as determined using RECIST v1.1 criteria or death due to any cause, whichever occurs first.

The following censoring rules will be applied to DOR:

- Participants who do not progress or die will be censored on the date of their last evaluable tumor assessment.
- Participants who started a new anticancer therapy without a prior reported progression will be censored on the date of their last evaluable tumor assessment on or prior to the initiation of first subsequent anticancer therapy.

Jazz Pharmaceuticals, Inc.

JZP712-201 Statistical Analysis Plan - Protocol Amendment

2

- Participants who are lost to follow-up or discontinued from the study without a prior reported progression and without start of subsequent anticancer therapy will be censored on the date of their last evaluable tumor assessment on or prior to the date of loss to follow-up or study discontinuation.

A by-participant listing will be presented including actual cohort, best response, duration of response, whether the participant was censored for duration of response, and if so, the reason.

[REDACTED]

[REDACTED]

[REDACTED]

[REDACTED]

## 10. SAFETY

Safety analyses will be based on the Safety Analysis Set.

### 10.1. Exposure

#### 10.1.1. Extent of Exposure

Exposure of study treatment (duration of exposure, number of cycles of treatment received, cumulative dose, dose intensity, and relative dose intensity) will be summarized by cohort and listed by participant using Safety analysis set.

The summary results will include the following:

- Number of cycles administered per participant (median, range)
- Number and percentage of participants with 1, 2, 3, 4, 5,  $\geq 6$  cycles administered
- Duration of lorbinecetin exposure (weeks), derived as  $[(\text{date of last dose} - \text{date of first dose}) + 1]/7$
- Cumulative lorbinecetin dose ( $\text{mg}/\text{m}^2$ ), calculated as sum of the doses received from the first cycle until the last cycle, including the dose received in the last cycle, and corrected by BSA
- Intended dose intensity ( $\text{mg}/\text{m}^2/\text{week}$ ), calculated as the planned dose per cycle divided by the planned number of weeks per cycle
- Absolute dose intensity ( $\text{mg}/\text{m}^2/\text{week}$ ), calculated as the cumulative lorbinecetin dose divided by the number of weeks of treatment, where the number of weeks of treatment is derived as  $[(\text{date of last dose} - \text{date of first dose}) + 21]/7$

Jazz Pharmaceuticals, Inc.

JZP712-201 Statistical Analysis Plan - Protocol Amendment

2

- Relative dose intensity (%), calculated as the ratio of absolute dose intensity divided by the intended dose intensity
- Number and percentage of participants with dose reduction (at least one, 1 dose reduction, 2 dose reductions); reasons for dose reductions will be included in by-participant data listing only
- Number and percentage of participants with incomplete infusions (i.e., infusions noted as interrupted and not restarted on eCRF) at least once, 1 time, 2 times, 3 or more times)

### 10.1.2. Treatment Compliance

Not applicable.

## 10.2. Adverse Events

Adverse events recorded in the CRF will be coded to SOC and PT using MedDRA version 25.0.

Unless otherwise noted, the AE summaries will be provided by SOC and PT; SOCs will be ordered alphabetically, with PTs within an SOC sorted in descending order of frequency. A participant will be counted only once at each level of summarization. If a participant has multiple episodes of events coded to the same preferred term, the participant will be counted just once while summarizing for that preferred term and at maximum severity (when applicable).

All AE summary tables will be generated overall (across all cohorts).

### 10.2.1. Treatment Emergent Adverse Events (TEAEs)

Treatment-emergent adverse events (TEAE) are defined as AEs with an onset date on or after the date of the first dose of the study treatment and within 30 days of last dose received (the 30-day safety window). TEAEs can be pre-treatment AEs that worsen in CTCAE grade after the start of study treatment. For the purpose of determining treatment-emergent, incomplete and missing AE start dates will be imputed as specified in [Section 7.4.3](#).

Treatment-related AEs are those for which investigators answer “Yes” to the question “Is this adverse event related to study treatment [lurbinectedin]?” in the CRF. Events for which investigators do not record the relationship to lurbinectedin will be considered as related to lurbinectedin for summary purposes. By-participant listings for those events for which the investigator does not record relationship to lurbinectedin will show treatment relationship as missing.

The severity of AEs will be recorded using the Common Terminology Criteria for Adverse Events (CTCAE), version 5.0. Adverse events are graded by the investigator as Grade 1 (mild), Grade 2 (moderate), Grade 3 (severe), Grade 4 (life threatening), or Grade 5 (fatal). The severity grade of events for which the severity was not recorded will be categorized as “missing” for summaries and listings and will be considered the least severe for the purposes of sorting for data presentation.

The following summaries of TEAEs (number and percentage of participants) will be provided overall (across all cohorts) using Safety analysis set:

Jazz Pharmaceuticals, Inc.

JZP712-201 Statistical Analysis Plan - Protocol Amendment

2

- Summary of any TEAEs by worst CTCAE grade (any grade, grade 3-4, grade 5) presented by SOC/PT
- Summary of TEAEs by PT (decreasing frequency)
  - Any grade
  - Grade 3-4
  - $\geq$  Grade 3
- Summary of any non-serious TEAEs by worst CTCAE grade (any grade, grade 3-4, grade 5) presented by SOC/PT
- Summary of treatment-related TEAEs by worst CTCAE grade (any grade, grade 3-4, grade 5) presented by SOC/PT
- Summary of treatment-related TEAEs by PT (decreasing frequency)

A by-participant TEAE listing will be provided with participant identifier, cohort, SOC, PT, start date, end date, severity grade, seriousness, relationship to lurbinectedin, and outcome of the AE using Safety analysis set.

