5.5. Criteria for Treatment Continuation

Further treatment cycles (ie, Cycle 2 and after) will be administered Q3W if the participant fulfills all the retreatment criteria within 3 days prior to the scheduled lurbinectedin infusion (Table 3) and defined in Table 4.

Table 4: Criteria for Treatment Continuation (Cycle 2 and After)

Variable	Retreatment Criteria (Day 1)
Hemoglobin ^a	≥ 9 g/dL
ANC	≥ 1.5 × 10 ⁹ /L
Platelets	≥ 100 × 10 ⁹ /L
AST/ALT	≤ 3 × ULN; for participants with documented metastatic liver disease, AST and ALT levels ≤ 5 × ULN
Total serum bilirubin	≤ 1.5 × ULN
Serum creatinine	≤ 1.5 × ULN or creatinine clearance ≥ 30 mL/min
Events of rhabdomyolysis	Withhold for Grade 2; resume at same dose if Grade ≤ 1
Other nonhematological treatment-related AEs (except isolated increased GGT and/or AP; Grade 2 asthenia, constipation, alopecia, peripheral neuropathy, or nonoptimally treated nausea and/or vomiting)	Grade ≤ 1
Active infection (including sepsis) and/or bleeding (any grade)	Absence

Abbreviations: AE = adverse event; ALT = alanine aminotransferase; ANC = absolute neutrophil count; AP = alkaline phosphatase; AST = aspartate aminotransferase; GGT = gamma-glutamyltransferase; ULN = upper limit of normal.

^a Participants may receive packed red blood cells transfusion and/or erythropoietin treatment, if clinically indicated, to increase or maintain adequate hemoglobin levels.

If a participant does not meet the requirements for treatment continuation on Cycle 2 Day 1 or subsequent cycles, reassessments will be performed at least every 48 to 72 hours for evaluation of treatment continuation. Treatment can be withheld up to a maximum of 3 weeks. Lurbinectedin dose delay and reduction rules are presented in Section 6.7.

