7.1. Discontinuation of Study Intervention

In rare instances, it may be necessary for a participant to permanently discontinue study intervention. If study intervention is permanently discontinued, the participant will return to the site 30 days (± 7 days) later for an EOT visit, and the participant will be followed for OS. For participants who discontinue treatment due to reasons other than disease progression, death, withdrawal of consent from study, or lost to follow-up, radiographic assessment should continue until disease progression, initiation of new anticancer therapy, death, withdrawal of consent from study, EOT Visit, lost to follow-up, or study termination. A radiological tumor assessment will be performed at the EOT visit for these participants if not performed within 7 days of the last treatment assessment visit. See the SoA (Table 3) for data to be collected at the time of discontinuation of study intervention and follow-up and for any further evaluations that need to be completed.

A participant must be discontinued from study intervention for any of the following reasons:

- The participant requests to discontinue study intervention
- The participant has an AE that may compromise the participant's continued participation (see Section 8.4.3 for follow-up guidelines)
- The participant experiences a Grade ≥ 3 hypersensitivity reaction
- The participant experiences Grade ≥ 3 rhabdomyolysis
- The participant has any of the clinical conditions as noted in Section 6.7, which cannot be resolved with either of the following attempts:
 - The participant requires > 2 dose reductions
 - The participant requires a treatment delay > 3 weeks from the due date because of treatment-related toxicity (except if objective clinical benefit is observed, with the Sponsor's agreement)
- The participant has a positive serum pregnancy test or becomes pregnant during the study (Appendix 5 and Section 8.4.5)
- The participant is noncompliant with study intervention or procedures
- The sponsor decides to terminate the study or an individual cohort for any reason
- The investigator determines the participant should not continue on study intervention

- The participant has confirmed radiological disease progression as per RECIST v1.1

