8.4.1. Time Period and Frequency for Collecting AE and SAE Information

All AEs and SAEs will be collected from the start of intervention until the EOT or E/D visit as specified in the SoA (Table 3) and per Section 8.4.3. Participants' discontinuation from study treatment with an ongoing treatment-related AE should be followed until satisfactory resolution per the investigator. Any spontaneous reporting of treatment-related SAE during the OS follow-up will be also collected and reported.

Note: All SAEs that occur after the consent form is signed but before study intervention/treatment must be reported by the investigator if they cause the participant to be

excluded from the trial, or are the result of a protocol-specified intervention, including but not limited to diet, placebo treatment, or a procedure.

Medical occurrences that begin before the start of study intervention but after obtaining informed consent will be recorded as Medical History/Current Medical Conditions, not as AEs.

All SAEs will be recorded and reported to the sponsor or designee immediately and within 24 hours of first knowledge of the event by study personnel, as indicated in [Appendix 4](#). The investigator will submit any updated SAE data to the sponsor within 24 hours of it being available. All treatment-related deaths will be reported as SAEs. Deaths due to progression of disease are not SAEs and should not be reported as SAEs.

Investigators are not obligated to actively seek information on new AEs or SAEs after conclusion of the study participation. However, if the investigator learns of any SAE, including a death, at any time after a participant has been discharged from the study, and he/she considers the event to be reasonably related to the study intervention or study participation, the investigator should promptly notify the sponsor.

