9.4.1.1.2. Post-baseline

Post baseline evaluations will be defined as evaluations taken after the date of the first dose of study treatment.

The post-baseline period is further characterized into a treatment period, a 30-day safety follow-up period after the last dose of study treatment, and an OS Follow-up Period.

Treatment-emergent adverse events are defined as AEs with an onset date on or after the date of the first dose of study treatment. An AE is a TEAE if it occurs up to 30 days after the last dose of study intervention. TEAEs can be pre-treatment AEs that worsen in CTCAE grade after the start of study treatment.

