### **10.2.3. TEAEs Leading to Study Treatment Discontinuation**

TEAEs leading to study treatment discontinuation are those with “Action Taken with Study Treatment = Drug Withdrawn” recorded in the CRF.

The following summaries of TEAEs leading to study treatment discontinuation (number and percentage of participants) will be provided across the cohorts using Safety analysis set:

- Summary of TEAEs leading to study treatment discontinuation by worst CTCAE grade (any grade, grade 3-4, grade 5) presented by SOC/PT
- Summary of treatment-related TEAEs leading to study treatment discontinuation by worst CTCAE grade (any grade, grade 3-4, grade 5) presented by SOC/PT

Jazz Pharmaceuticals, Inc.

JZP712-201 Statistical Analysis Plan - Protocol Amendment

2

The analyses will be conducted from the first dosing date of study treatment to the last date of the 30-day safety window.

All TEAEs leading to study treatment discontinuation will be included in a by-participant listing including but not limited to participant identifier, cohort, SOC, PT, start date, end date, severity grade, relationship to lorbinecetin, seriousness, and outcome of the AE using Safety analysis set.

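### The 30-day TEAE window is shorter than an allowed dose hold, so an event that starts 31 to 42 days after the last dose, with no later dose, drops out of the safety tables

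*SAP*

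**What the plan says.** - **Window.** SAP 10.2.1 requires onset on or after the first dose of study "treatment and within 30 days of last dose received (the 30-day safety window"). SAP 7.3.1 agrees, and the rule comes from Protocol 9.4.1.1.2: "An AE is a TEAE if it occurs up to 30 days after the last dose of study intervention".
- **Study periods.** SAP 7.2.2 ends the treatment period at the last dose, adds a 30-day safety period, and assigns everything later to survival follow-up.
- **Tables and listings.** SAP 10.2.3 states: "The analyses will be conducted from the first dosing date of study treatment to the last date of the 30-day safety window". Sections 10.2.2 (SAEs) and 10.2.4 (dose modification) carry the same limit, and the overview in 10.2.7 counts TEAEs. The listings in 10.2.1 and 10.2.3 are also of TEAEs.
- **Holds.** Protocol 5.5: "Further treatment cycles (ie, Cycle 2 and after) will be administered Q3W" if retreatment criteria are met; otherwise, "Treatment can be withheld up to a maximum of 3 weeks". Protocol 7.1 shows where the clock starts. Treatment stops if "The participant requires a treatment delay > 3 weeks from the due date because of treatment-related toxicity", with an exception for documented benefit. Protocol 6.7 allows longer delays case by case.
- **Collection.** Protocol 8.4.1: "All AEs and SAEs will be collected from the start of intervention until the EOT or E/D visit".
- **Worsening.** Protocol Appendix 4 has a rise in severity recorded as a new AE, with its own start.

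**The concern.** The analysis window and the hold rules run on different clocks. The window counts from the last dose received. The hold counts from the date on which the next dose was due, which is already three weeks later. During a hold the participant is reassessed every 48 to 72 hours for the next infusion (Protocol 5.5) and is on treatment in any ordinary sense. From day 31, however, SAP 7.2.2 places that participant in survival follow-up.

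The result is that classification depends on what happens afterwards. If dosing resumes, the last-dose date moves forward and the event is counted. If it does not, the same event with the same onset day is left out. This can only lower the counts.

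Safety is a secondary objective. The tables at risk include those for SAEs and for events leading to discontinuation. A visible mismatch is also possible: SAP 8.2 takes the primary reason for stopping treatment from the CRF with no 30-day limit, so disposition could show a stop for an adverse event that the 10.2.3 table omits. By contrast, SAP 7.4.3 counts an event with a completely missing start date as treatment-emergent.

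**Working it through.** The plan's 30 days is a definition, so there is no figure to reproduce. The check is a day count, with the last dose as day 0. An event is a TEAE if first dose ≤ onset ≤ last dose received + 30.

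**Inputs**
- Cycle length: 21 days (Protocol 5.5).
- Longest regular delay: 21 days (Protocol 5.5), counted from the due date (Protocol 7.1).
- Window after last dose: 30 days (SAP 7.3.1 and 10.2.1; Protocol 9.4.1.1.2).

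**Size of the gap**
- End of the longest regular hold: 21 + 21 = day 42.
- Part of a delay that the window covers: 30 − 21 = 9 days.
- Days not covered: 42 − 30 = 12 (days 31 to 42).
- Share of a full delay: 12/21 = 57%. (Dividing by 42 gives 29%, but that is a share of the time since the last dose, not of the hold.)

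| Delay past due date (days) | Hold ends on day | Days not covered |
|---|---|---|
| 7 | 28 | 0 |
| 9 | 30 | 0 |
| 10 | 31 | 1 |
| 14 | 35 | 5 |
| 21 | 42 | 12 |

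If the +3-day dosing window in the Schedule of Activities is added, the hold ends on day 45. Then 15 of 24 days (62.5%) are uncovered. Case-by-case delays have no stated upper limit.

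**Classification of three events**
- Onset day 25, no further dose: 25 ≤ 30, a TEAE.
- Onset day 35, no further dose: 35 > 30, not a TEAE.
- Onset day 35, next dose on day 42: the limit becomes 42 + 30 = 72, a TEAE.

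**A route within the protocol's own rules.** Table 4 withholds treatment for Grade 2 rhabdomyolysis, and Sections 6.7 and 7.1 discontinue for Grade ≥ 3. If the worsening happens on day 35, Appendix 4 makes it a new AE starting that day. The earlier Grade 2 record stays a TEAE. The Grade 3 record, the one that triggers withdrawal, does not qualify.

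**Is the event recorded?** Collection runs to the EOT or E/D visit, but the protocol times EOT in two ways:
- Schedule of Activities: 30 ± 7 days after the last dose, so days 23 to 37.
- Protocol 7.1: 30 ± 7 days after permanent discontinuation. For a stop on day 42, that is days 65 (42 + 23) to 79 (42 + 37).

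Under Section 7.1 the whole gap is inside the collection period. Under a literal reading of the Schedule, its last days might not be.

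**The case against.** The strongest reply is that nothing here is inconsistent. Thirty days is a conventional window, it is prespecified, and the SAP follows the protocol exactly. That stands: this is a choice of definition, not a conflict between documents, and changing it departs from Protocol 9.4.1.1.2. It does not explain why the window should be shorter than the hold that the same protocol allows.

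The reply also limits how far the point reaches. A reader might draw three stronger conclusions that the documents do not support:

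- **That adverse events ending treatment after a hold are generally missed.** A hold begins because retreatment criteria fail within 3 days before the due date, about days 18 to 21. The toxicity behind it has normally begun by day 30. If that record carries the withdrawal, it is a TEAE and appears in 10.2.3.
- **That only events preventing re-dosing are lost.** Any onset after day 30 with no later dose is excluded, including in someone who stops for progression or withdraws consent.
- **That the event disappears from the report.** SAP 10.2.5 summarises all deaths without the 30-day limit. Protocol 9.4.4.1 provides for listing all AE data. The SAE listing in SAP 10.2.2 is not expressly limited to TEAEs, although the 30-day sentence there leaves it unclear. The loss is from the summary tables and from the SAP's TEAE and discontinuation listings.

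**Conclusion.** The point holds in limited form. The TEAE window leaves days 31 to 42 of the longest regular hold uncovered: 12 days, or 57% of a full delay, and more where a longer delay is agreed. Delays of up to 9 days leave no gap. Within the gap, a new AE or a grade increase recorded as a new AE is counted or dropped according to whether another dose follows. The direction is always towards undercounting.

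This rests on the delay being counted from the due date, as Protocol 7.1 states, and on neither document extending the window during a hold; no such extension was found.

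How many participants this would affect cannot be estimated, because the documents give no rate of long holds or of new events during them. A reader might infer a material bias in the discontinuation or SAE rates; the documents show the mechanism and its direction, not its size. The change is still worth making, because it corrects a rule that depends on later dosing and costs little.

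**What to change.** - In SAP 7.3.1 and 10.2.1, end the TEAE window at the later of (a) 30 days after the last dose and (b) the recorded date of the decision to discontinue study treatment permanently. Date (b) should not extend the window past the start of new anticancer therapy.
- In SAP 10.2.3, count any AE whose recorded action is drug withdrawn, whatever its onset day.
- Use the same end date in SAP 10.2.2, 10.2.4 and 10.2.7. Section 10.2.5 needs no change, since all deaths are already summarised.
- Record the departure from Protocol 9.4.1.1.2 in SAP 7.8, which now reports no changes.
- Do not tie the window to the EOT visit. The Schedule of Activities and Protocol 7.1 time that visit differently, and the two must be reconciled.

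The cost is one definition and one derivation. SAP 8.2 already draws treatment discontinuation from the CRF, but the documents do not say that the date of the decision is captured, so this should be confirmed. The downside is small: a few more events are counted than under the plain 30-day convention. No change to the hold rules is proposed.

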### **10.2.2. Serious Adverse Events (SAEs)**

Serious AEs are those for which investigators answers “Yes” to the question “Was the adverse event serious?” in the CRF. The clinical database will be reconciled with the SAE database before the final database lock.

The following summaries of SAEs (number and percentage of participants) will be provided across the cohorts using Safety analysis set:

- Summary of SAEs by worst CTCAE grade (any grade, grade 3-4, grade 5) presented by SOC/PT
- Summary of treatment-related SAEs by worst CTCAE grade (any grade, grade 3-4, grade 5) presented by SOC/PT

All analyses will be conducted from the first dosing date of study treatment to the last date of the 30-day safety window.

A by-participant SAE listing will be provided using Safety analysis set.

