9.4.4.1. Adverse Events

Adverse events will be coded using MedDRA to classify events under primary system organ class and preferred term; the severity will be graded using the NCI CTCAE v5.0.

The number and percentage of participants who experienced TEAEs, treatment emergent SAEs, TEAEs by maximum severity, TEAEs leading to discontinuation of study drug, Grade 3 and 4 TEAEs, treatment-related TEAEs, treatment-related SAEs, treatment-related TEAEs leading to discontinuation of study drug, treatment-related Grade 3 and 4 TEAEs, and Grade 5 TEAEs will be summarized using the Safety analysis set. Results will be presented by SOC and preferred term, or preferred term only. Summary will be separate and in an overview.

All deaths will be summarized and listed.

For all AE summaries, if a participant has more than 1 AE within a preferred term, the participant is counted only once at the maximum severity and with the closest relationship to study drug. If a participant has more than 1 AE within a SOC, the participant is similarly counted once when reporting results for that SOC.

All AE data will be listed. Listing of AEs will include all enrolled participants as pretreatment SAEs and deaths are collected. The information presented will include participant number,

primary SOC and preferred term, date of onset, severity, relationship to study drug, action taken, and stop date (if available).

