## 6. ANALYSIS SETS

For purposes of analysis, the following populations are defined:

Analysis Set	Description
Enrolled	All participants who sign the informed consent form (ICF).
Safety	All participants who took at least one dose of study treatment. This is the primary set for safety analyses.
Efficacy evaluable	Participants in Safety analysis set with measurable disease at baseline and one of the following: (a) at least one post-baseline evaluable tumor assessment, (b) clinical progressions, or (c) death.
[REDACTED]	[REDACTED]
[REDACTED]	[REDACTED]

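### The SAP's AE and SAE listings omit never-dosed participants whom the protocol includes, and related SAEs collected more than 30 days after the last dose are not tabulated

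*SAP*

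**What the plan says.** **What the protocol collects.** Section 8.4.1 makes certain SAEs reportable before dosing: "All SAEs that occur after the consent form is signed but before study intervention/treatment must be reported by the investigator", provided that they exclude the participant or result from something the protocol itself required. Other occurrences between consent and first dose go to medical history. Routine collection then runs from the start of treatment to the end-of-treatment (EOT) or early-discontinuation visit. After that, "Any spontaneous reporting of treatment-related SAE during the OS follow-up will be also collected and reported". Section 5.4 adds that any SAE belongs to the minimum data kept on a screen failure.

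**What the protocol plans to output.** Section 9.4.4.1 summarises SAEs on the Safety set. It names treatment-emergent SAEs and, as a separate item, treatment-related SAEs. For listings it is broader: "Listing of AEs will include all enrolled participants as pretreatment SAEs and deaths are collected".

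**What the SAP plans.** The by-participant TEAE listing in 10.2.1 uses the Safety set. For SAEs, 10.2.2 has three relevant sentences:

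- Tables: "The following summaries of SAEs (number and percentage of participants) will be provided across the cohorts using Safety analysis set".
- Window: "All analyses will be conducted from the first dosing date of study treatment to the last date of the 30-day safety window".
- Listing: "A by-participant SAE listing will be provided using Safety analysis set".

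SAP Section 6 defines the Safety set as "All participants who took at least one dose of study treatment"; the Enrolled set is everyone who signed consent. SAP 7.8 records no changes to planned analyses.

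**The concern.** The protocol gives a reason for its wider listing population: it collects serious events that can happen before any drug is given. An SAE that excludes someone before dosing happens, by definition, in a person who is never dosed. A listing confined to dosed participants cannot show that event, so the SAP removes the very group for which the protocol widened the listing, and does so without recording a departure.

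The second matter is how later drug-attributed events are displayed. The investigator reports them and the sponsor holds them, yet both SAE tables stop 30 days after the last dose. The titles speak of SAEs and treatment-related SAEs with no treatment-emergent qualifier, so a reader of the report could take the related-SAE table as complete.

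Safety is a secondary endpoint, the study has one arm, the initial cohorts have at most 20 participants, and there is no data monitoring committee. A single related SAE is visible at that scale. No efficacy result or cohort decision rule depends on this point.

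**Working it through.** The plan states no figure to reproduce. The check sets the SAP's population and window for each SAE output against what the protocol collects.

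**Step 1. Inputs.**

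- Table population: Safety set (SAP 10.2.2).
- Table window: first dose to 30 days after last dose (SAP 10.2.2). This is counted from the last dose; it is not study day 30.
- Listing population: Safety set (SAP 10.2.1 for TEAEs, 10.2.2 for SAEs), against all enrolled participants (protocol 9.4.4.1).
- EOT visit: 30 ± 7 days after last dose (protocol 7.1 and Table 3).

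**Step 2. The only arithmetic.** The EOT visit may fall between 30 − 7 = day 23 and 30 + 7 = day 37 after the last dose. Routine SAE collection can therefore run up to 37 − 30 = 7 days past the table window.

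**Step 3. Follow each type of SAE through the SAP outputs.**

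| SAE that the protocol collects | SAE tables | SAE listing | Agrees with protocol 9.4.4.1? |
|---|---|---|---|
| Before first dose, never dosed | No | No | Tables yes; listing no |
| Before first dose, later dosed | No | Possible | Tables yes; listing possible |
| Days 31 to 37 after last dose, before a late EOT visit | No | Possible | No window stated for related SAEs |
| Treatment-related, reported spontaneously in survival follow-up | No | Possible | No window stated for related SAEs |

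The listing entries read *possible* because the window sentence speaks of analyses, and the listing sentence that follows it carries no window. The SAP does not say whether one governs the other.

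**Step 4. Other outputs that might show the first row.** SAP 8.1 reports screen failures on the Enrolled set, with adverse event among the reasons, but specifies no event term, grade or outcome. SAP 10.2.5 lists deaths for all enrolled participants, so a fatal case would appear there. A non-fatal SAE in a never-dosed participant has no other specified output.

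**Step 5. Consistency within the SAP.** The deaths listing uses the enrolled population and the SAE listing does not. The protocol sentence gives pretreatment SAEs and deaths together as its reason, and the SAP has carried over the deaths part only.

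**The case against.** Several points on the other side are sound.

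- **Tables and pretreatment events.** A reader might infer that the SAE tables should include pretreatment SAEs. The documents do not support this. Protocol 9.4.4 puts all safety analyses on the Safety set, 9.4.4.1 plans a table of treatment-emergent SAEs, and 9.4.1.1.2 defines treatment-emergent by the same 30-day limit. The sentence on enrolled participants concerns listings alone. This objection stands in full.
- **Late related SAEs in the main count.** A reader might infer that every later related SAE must be added to the incidence. The protocol does not promise that: it names treatment-related SAEs among TEAE categories and gives no window. After the EOT visit only spontaneous reports of related events arrive, so merging them would mix systematic with unsystematic collection. SAP 10.2.7 also counts serious events as TEAEs, and an unwindowed table could disagree with it. Keeping the window for the main count is defensible. What remains is that the titles do not disclose the cut and no row or note shows the later events.
- **Events thrown away.** A reader might conclude that the plan loses these events altogether. It does not. Late SAEs in dosed participants can still be listed, the screen-failure and deaths outputs cover part of the pretreatment group, and 10.2.2 requires reconciliation with the SAE database before final lock.
- **Size.** One might set the one-month window against the roughly six months of projected survival follow-up and infer that most related SAEs fall outside it. That compares calendar time, not events. Follow-up also varies with deaths and withdrawals, and it ends if a cohort closes for futility.

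None of this answers the listing point. The two documents name different populations for the same output, and SAP 7.8 says nothing has changed.

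**Conclusion.** The point holds in two parts of unequal strength.

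1. **Firm.** The AE and SAE listing population in the SAP contradicts the protocol. A reportable non-fatal SAE before dosing in a never-dosed participant reaches no SAE listing. This follows from the definitions of the analysis sets and needs no assumption about event rates.
2. **Smaller.** The treatment-related SAE table ends 30 days after the last dose, while the protocol collects related SAEs beyond that and routine collection can reach day 37. This is a gap in labelling and display, not a proven conflict. It rests on reading the protocol's separate mention of treatment-related SAEs as not limited to treatment-emergent events, which its wording allows but does not compel.

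The number of events cannot be derived from the documents. It is probably small: only some pre-dose SAEs are reportable, and late reports are spontaneous. The change should be made because it restores agreement with the protocol at almost no cost.

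**What to change.** In SAP 10.2.1 and 10.2.2:

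1. Run the AE and SAE listings on the Enrolled set, as protocol 9.4.4.1 states. Flag each event as pretreatment, treatment-emergent or post-window, and state that the 30-day window does not restrict the listings.
2. Keep the windowed tables on the Safety set, but label them treatment-emergent so that they match the serious-TEAE rows in 10.2.7. Show treatment-related SAEs with onset more than 30 days after the last dose in a separate row or footnote, outside the main incidence.

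If the sponsor prefers to keep the Safety set for the listings, SAP 7.8 should record the departure and give the reason.

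The cost is a few SAP sentences, revised table titles and slightly longer listings. A few more related SAEs may be displayed. The protocol already collects the data, and no sample size, efficacy analysis or cohort rule changes.
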